3.3. Study Treatments

The study will feature multiple parts: Part A, Part B, and Part C. The planned *nominal* doses are provided below by treatment group.

[figure not shown]
In Part A, approximately 36 participants who meet all eligibility criteria will be randomized in a 1:1:1 ratio into one of the following 3 treatment groups:

Treatment Group 1: 31 mg inhaled Remdesivir for Injection formulation daily for 5 days

Treatment Group 2: 31 mg inhaled Remdesivir for Injection formulation daily for 3 days followed by PTM daily for 2 days

Treatment Group 3: PTM daily for 5 days

Part A

[figure not shown]
In Part B, if supported by Phase 1a data in healthy volunteers, an additional 36 participants who meet all eligibility criteria may be randomized in a 1:1:1 ratio into one of the following treatment groups:

Treatment Group 4: 62 mg inhaled Remdesivir for Injection formulation daily for up to 5 days

Treatment Group 5: 62 mg inhaled Remdesivir for Injection formulation daily for up to 3 days followed by PTM through Day 5

Treatment Group 6: PTM daily for 5 days

Part B

In Parts A and B, at in-clinic screening, after the participant has provided informed consent, assessments will include but are not limited to the following: demographic and baseline characteristics, medical history, and concomitant medications will be documented. Body weight and height will be measured. A urine pregnancy test will be performed for women of childbearing potential. Vital signs including heart rate, temperature, blood pressure, and SpO₂ will be recorded. A complete physical examination will be performed.

[figure not shown]
Participants with PCR-confirmed COVID-19 who enroll in the study will return to clinic daily on Days 1 through 5 for study treatment administration and clinical assessments. Participants will return to clinic on Days 7 and 14 for follow-up clinical assessment and undergo a Day 28 follow-up which may be completed by telephone.

Part C

Part C of the study will include an expanded safety and efficacy assessment of an additional 80 participants. Participants in Part C will be enrolled after review of preliminary safety data from Parts A and B through at least Day 7. Approximately 80 participants will be randomized 3:1 to 1 of 2 treatment groups:

Treatment Group 7: 39 mg Remdesivir for Inhalation Solution formulation once daily for 5 days by mouthpiece

Treatment Group 8: PTM daily for 5 days by mouthpiece

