5. INVESTIGATIONAL MEDICINAL PRODUCTS

5.1. Randomization, Blinding, and Treatment Codes Access

5.1.1. Randomization

In Part A, approximately 36 participants who meet eligibility criteria will be randomized in a 1:1:1 ratio to receive either of two inhaled 31 mg RDV regimens or PTM starting on Day 1 using an interactive voice/web response system (IXRS) and assigned a subject number. In Part B, an additional 36 participants who meet eligibility criteria will be randomized in a 1:1:1 ratio to receive either of two inhaled 62 mg RDV regimens or PTM starting on Day 1 using an IXRS and assigned a subject number.

In Part C, approximately 80 participants will be randomized 3:1 to 1 of 2 treatment groups to receive either: Remdesivir for Inhalation Solution formulation (nominal dose of 39 mg to achieve 10 mg deposited dose) administered by mouthpiece or PTM administered by mouthpiece starting on Day 1 using an IXRS and assigned a subject number.

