8.5. Efficacy Analysis

8.5.1. Primary Analysis

SARS-CoV-2 viral load will be summarized by treatment using descriptive statistics in Part A and Part B. For Part C, time weighted average change in SARS-CoV-2 viral load will be compared between the RDV and placebo groups using analysis of covariance with baseline viral load included in the model as a covariate.

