3.7. Data Handling Conventions and Transformations

In general, age collected at Day 1 (in years) will be used for analyses and presented in listings. If age at Day 1 is not available for a participant, then age derived based on date of birth and the Day 1 visit date will be used instead. If an enrolled participant was not dosed with any study drug, the randomization date will be used instead of the Day 1 visit date. For screen failures, the date the first informed consent was signed will be used for the age derivation.

Laboratory data that are continuous in nature but are less than the lower limit of quantitation (LOQ) or above the upper LOQ will be imputed as follows:

- A value that is 1 unit less than the LOQ will be used to calculate descriptive statistics if the datum is reported in the form of “ $< x$ ” (where x is considered the LOQ). For example, if the values are reported as < 50 and < 5.0 , values of 49 and 4.9, respectively, will be used to calculate summary statistics. An exception to this rule is any value reported as < 1 or < 0.1 , etc. For values reported as < 1 or < 0.1 , a value of 0.9 or 0.09, respectively, will be used to calculate summary statistics.
- A value that is 1 unit above the LOQ will be used to calculate descriptive statistics if the datum is reported in the form of “ $> x$ ” (where x is considered the LOQ). Values with decimal points will follow the same logic as above.
- The LOQ will be used to calculate descriptive statistics if the datum is reported in the form of “ $\leq x$ ” or “ $\geq x$ ” (where x is considered the LOQ).

SARS-CoV-2 viral load results that are below LOQ but have a positive signal will be reported as “ $< 2228\text{cp/mL SARS-CoV-2 detected}$ ” (nasopharyngeal/oropharyngeal swabs) or “ $<1390\text{cp/mL SARS-CoV-2 detected}$ ” (saliva) and those that are below LOD and negative will be reported as “No SARS-CoV-2 detected”. The data will be imputed as follows:

- A value of 1114 copies/ml (1/2 of the LOQ of 2228 copies/ml) will be used to calculate descriptive statistics if the datum is reported as “ $< 2228\text{cp/mL SARS-CoV-2 detected}$ ” from nasopharyngeal/oropharyngeal swab sample.
- A value of 746.5 copies/ml (1/2 of the LOD of 1493 copies/ml) will be used to calculate descriptive statistics if the datum is reported as “No SARS-CoV-2 detected” from nasopharyngeal/oropharyngeal swab sample.

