- A value of 695 copies/ml (1/2 of the LOQ of 1390 copies/ml) will be used to calculate descriptive statistics if the datum is reported as “ $< 1390\text{cp/mL SARS-CoV-2 detected}$ ” from saliva sample.
- A value of 501 copies/ml (1/2 of the LOD of 1002 copies/ml) will be used to calculate descriptive statistics if the datum is reported as “No SARS-CoV-2 detected” from saliva sample.

Any SARS-CoV-2 viral load samples collected on or after the participants are receiving additional COVID-19 treatments (see [Appendix 2](#)) will be excluded from the viral load analysis.

Patients with negative viral load at baseline are not included in the viral load analysis.

Base 10 logarithm transformation will be used for analyzing SARS-CoV-2 viral load.

Sparse PK concentration values that are below the limit of quantitation (BLQ) will be presented as “BLQ” in the data listing.

Natural logarithm transformation will be used for analyzing concentrations. Concentration values that are BLQ will be presented as “BLQ” in the concentration data listing. For intensive PK concentration, values that are BLQ will be treated as 0 at predose time points, and one-half the value of the LOQ at postdose time points for summary purpose. For predose or postdose timepoint of sparse PK and single anytime PK, values that are BLQ will be treated as one-half the value of the LLOQ for summary purpose.

The following conventions will be used for the presentation of summary and order statistics:

- If at least 1 subject has a concentration value of BLQ for the time point, the minimum value will be displayed as “BLQ.”
- If more than 25% of the subjects have a concentration data value of BLQ for a given time point, the minimum and Q1 values will be displayed as “BLQ.”
- If more than 50% of the subjects have a concentration data value of BLQ for a given time point, the minimum, Q1, and median values will be displayed as “BLQ.”
- If more than 75% of the subjects have a concentration data value of BLQ for a given time point, the minimum, Q1, median, and Q3 values will be displayed as “BLQ.”
- If all subjects have concentration data values of BLQ for a given time point, all order statistics (minimum, Q1, median, Q3, and maximum) and summary statistics will be displayed as “BLQ.”

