	Total Bilirubin	Increase	Total Bilirubin (Hyperbilirubinemia)
	Uric Acid	Increase	Uric Acid (Hyperuricemia)
	Prothrombin Intl. Normalized Ratio (INR)	Increase	Prothrombin Intl. Normalized Ratio (Increased)
	Activated partial thromboplastin time (aPTT)	Increase	Activated partial thromboplastin time (Increased)
	Prothrombin Time (PT)	Increase	N/A

17) The first Part B participant was screened on Oct 29, 2020 and the first Part C participant was screened on Jan 24, 2021. Screen failure participants of each study part is derived from scrndt,

```
if part=" then do;  
  if .< scrndt <29Oct2020 then part='Part A';  
  else if scrndt >= 29Oct2020 & scrndt <24Jan2021 then part='Part B';  
  else part='Part C';  
end;
```

18) SARS-CoV-2 viral load from nasopharyngeal and oropharyngeal swabs and saliva samples were to be collected. SARS-CoV-2 viral load in nasopharyngeal and oropharyngeal swabs and saliva samples will be analyzed separately.

- a) For numeric SARS-CoV2 summary (e.g, mean viral load, change from baseline etc.), “Inconclusive” SARS-CoV2 result is set to missing.
- b) For categorical SARS-CoV2 summary, 3 categories will be included, i.e. Positive, Inconclusive, and Negative.
 - i) Positive = any numeric result or “<LLOQ SARS-CoV2 detected” - LLOQ could vary by sample type
 - ii) Negative = “No SARS-CoV2 detected”
 - iii) Inconclusive = “Inconclusive”
- c) For Negative SARS-CoV2 confirmation, “Inconclusive” SARS-CoV2 result will not be considered as missing thus a “Negative” followed by a “Inconclusive” is NOT confirmed.
- d) 2 negative results from the same day do not equal confirmation.
- e) If last PCR sample is negative for participants completed the study or for participant withdrawn early from the study, then one negative PCR of last sample is considered as confirmed negative.
- f) Categorical SARS-CoV2 and SARS-CoV2 negative summary will be separated out by sample type. There will be no combined positive or negative category using 2 or more sample types.

19) SAS code for ANCOVA analysis of DAVG:

```
ods output ParameterEstimates=out1 LSMeans=out2 LSMeanCL=out3  
LSMeanDiffCL=out4;  
proc glm data=dat1 plots=none;  
  class trt01pn;  
  model DAVG = trt01pn base / solution;  
  lsmeans trt01pn / stderr cl pdiff;  
run;  
ods output close; quit;
```

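### The Part C DAVG7 ANCOVA pools the residual variance across a 3:1 split, so its standard error and interval are right only if both arms are equally variable

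*Protocol*

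**What the plan says.** Protocol 3.3 sets the Part C allocation: "Approximately 80 participants will be randomized 3:1 to 1 of 2 treatment groups". With about 80 participants this is 60 on RDV and 20 on placebo, before the mFAS removes those negative at baseline.

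Protocol 8.5.1 says DAVG7 will be "compared between the RDV and placebo groups using analysis of covariance with baseline viral load included in the model as a covariate". It does not name a variance structure. SAP 6.1.3 repeats the ANCOVA for Part C and, after a check of poolability, extends it to the pooled groupings of SAP 3.2.

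The variance structure is fixed only in the PROC GLM code of SAP Appendix 2 item 19: "model DAVG = trt01pn base / solution", followed by "lsmeans trt01pn / stderr cl pdiff". The standard error, confidence limits (95% by SAS default) and p-value therefore all come from one pooled mean square.

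SAP 3.7 gives fixed values to low swab results. For a non-detect: "A value of 746.5 copies/ml (1/2 of the LOD of 1493 copies/ml) will be used to calculate descriptive statistics". For a detected result below the LOQ: "A value of 1114 copies/ml (1/2 of the LOQ of 2228 copies/ml) will be used to calculate descriptive statistics". Saliva has its own pair of values. No robust variance, arm-specific variance or censored-data model for this comparison appears in the text of either document.

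**The concern.** Pooling the variance does little harm when the arms are of equal size, but it is not protected at 3:1. About three quarters of the pooled variance comes from the RDV arm, while about three quarters of the true variance of the difference comes from the small placebo arm. If the two residual variances differ, the reported precision is wrong.

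There is a concrete reason why they might differ. Samples at the floor all take the same value, so an arm that clears more virus loses spread. If that is the larger RDV arm, the standard error comes out too small. If instead some participants respond to RDV and others do not, the RDV arm gains spread and the standard error comes out too large. In a study with about 20 placebo participants and no power calculation, the interval around the difference is the result that readers will rely on most.

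**Working it through.** **Inputs from the documents.** n = 60 and 20. Model: treatment plus baseline. Swab substitutions 746.5 copies/mL (2.873 log10) and 1114 copies/mL (3.047 log10). Part C samples after baseline on Days 3, 5 and 7. Participants negative at baseline are excluded. The documents give no SD, effect size, share of non-detects, power or standard error, so there is no figure of the plan's own to reproduce.

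**Step 1: formula.** Let r be the residual variance in the RDV arm divided by that in the placebo arm, with the placebo variance set to 1.

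- Variance used by the model: [(59r + 19)/78] × (1/60 + 1/20)
- True variance of the difference: r/60 + 1/20

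Example, r = 0.7. Model: (41.3 + 19)/78 × 0.06667 = 0.05154. True: 0.01167 + 0.05 = 0.06167. Ratio of standard errors: √(0.05154/0.06167) = 0.914.

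| r | Model SE / true SE | Approximate coverage |
|---|---|---|
| 0.5 | 0.843 | 90.7% |
| 0.7 | 0.914 | 93.1% |
| 0.8 | 0.945 | 94.0% |
| 0.9 | 0.974 | 94.7% |
| 1.0 | 1.000 | 95.4% |
| 1.25 | 1.058 | 96.5% |

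The approximation gives 95.4% at r = 1, so its coverage column reads about 0.4 points high. At 40:40 the model variance is [(39r + 39)/78] × (2/40) = (r + 1)/40, which equals the true variance for every r. The unequal split is therefore necessary for the problem.

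**Step 2: what the floor does to r when the effect is the same in everyone.** Simulation at 60:20 with the SAP trapezoid, swab substitutions and ANCOVA. Coverage is for the mean difference on the substituted scale.

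- Setting A (assumed): baseline mean 6 and SD 1.5 log10, decline 0.45/day with SD 0.2, assay noise SD 0.6; 4,000 trials.
- Setting B (assumed): baseline mean 5 to 7, baseline SD 1 to 2, decline 0.35 to 0.5/day with SD 0.2, assay/visit SD 0.7; 8,000 trials. The rows below use decline 0.35/day.

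| Setting | DAVG7 difference | Model SE / true SE | Coverage |
|---|---|---|---|
| A | 0 | – | 95.5% |
| A | -0.28 | – | 94.8% |
| A | -0.53 | 0.200/0.219 = 0.91 | 92.8% |
| A | -0.73 | 0.189/0.218 = 0.87 | 91.2% |
| B, mean 6 | 0 | 0.996 | 94.9% |
| B, mean 6 | -0.32 | 0.966 | 94.2% |
| B, mean 6 | -0.60 | 0.928 | 93.2% |
| B, mean 6 | -0.95 | 0.861 | 91.0% |
| B, mean 6 | -1.37 | 0.748 | 85.2% |
| B, mean 7 | -0.36 | 0.984 | 94.7% |
| B, mean 7 | -0.70 | 0.960 | 94.1% |
| B, mean 5 | -0.48 | 0.897 | 91.9% |
| B, mean 5 | -0.73 | 0.813 | 88.9% |

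With the substitution switched off, r = 1.00 and coverage is 95.0% whatever the uniform effect. In these runs the floor makes the variances unequal and the 3:1 split turns that into a wrong standard error.

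**Step 3: the other direction.** Setting B, baseline mean 6, with the RDV effect varying between participants:

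| SD of RDV effect (log10/day) | DAVG7 difference | Model SE / true SE | Coverage |
|---|---|---|---|
| 0.2 | -0.25 | 1.049 | 96.1% |
| 0.2 | -0.53 | 1.008 | 95.2% |
| 0.2 | -0.88 | 0.935 | 93.1% |
| 0.3 | -0.45 | 1.090 | 96.8% |
| 0.3 | -0.18 | 1.132 | 97.3% |

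With effect SD 0.3 and zero mean added decline, the ratio reached 1.17. The formula in Step 1 with an RDV SD 1.3 times the placebo SD (r = 1.69) gives √(0.10146/0.07817) = 1.14.

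**Step 4: does an unequal-variance standard error cure it?** A Welch-type standard error gave 94.2 to 95.0% coverage in every Setting B scenario, against 85 to 97% for the pooled variance. In Setting A, HC3 or arm-specific variances gave 94.0 to 95.6%.

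**Step 5: the pooled-group ANCOVA.** Planned totals are 24 + 24 + 60 = 108 on RDV and 12 + 12 + 20 = 44 on placebo. At r = 0.7 the model variance is (107 × 0.7 + 43)/150 × (1/108 + 1/44) = 0.02514, and the true variance is 0.7/108 + 1/44 = 0.02921. The ratio is √(0.02514/0.02921) = 0.93, so the same weakness is present.

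**The case against.** The strongest reply is that pooled-variance ANCOVA is conventional, that the study is early-phase and sized for description without multiplicity control, and that every magnitude above rests on assumed kinetics. For effects near -0.3 log10 the loss of coverage is mostly a point or less. All of this stands. It makes the matter a cheap improvement and not a fatal flaw.

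Three stronger readings are tempting, and the documents do not support them.

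- A reader might infer that the standard error is too small whenever RDV works. That needs a fairly uniform effect. Step 3 shows the error vanishing or reversing when response varies, and nothing in the documents says which case applies.
- A reader might infer that the test is invalid. The SAP 6.1.2 null is no difference. If RDV has no effect in any participant, the arms have equal variance and the test keeps its size. The issue is interval coverage and stated precision.
- A reader might infer that Protocol 8.5.1 is wrong. It names only the model and covariate, which are compatible with any variance structure.

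It can also be said that SAP 3.7 words its substitutions as being for descriptive statistics, so their use in the ANCOVA is not explicit. That is true. But DAVG7 needs a number for each sample, item 18 sets only inconclusive results to missing, and no other rule is given. Substitution is the natural reading.

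**Conclusion.** The point holds in a conditional, two-directional form. The Part C standard error and interval depend on an equal-variance assumption that a 60:20 split does not protect and that the substitution rule gives reason to doubt. With a uniform RDV effect of about -0.3 to -0.7 log10, the standard error is about 2 to 13% too small in the main settings and coverage is about 91 to 95%. Heavier flooring or larger effects go further, to 85% in the most extreme run. With RDV response varying strongly between participants, the standard error is roughly 15% too large (13 to 17% in the most variable runs).

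The mechanism follows from the allocation, the item 19 code and the substitution rule. The sizes rest wholly on assumed baseline load, decline, assay noise and effect distribution.

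The floor also pulls the estimate towards zero (-0.60 against -0.81 log10 without it, in Setting B with baseline mean 6). That is a separate matter, and a change of variance estimator does not correct it.

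**What to change.** In SAP 6.1.3 and Appendix 2 item 19, keep treatment and baseline viral load as the model, but take the standard error, interval and p-value from a variance that does not assume equal arms. Either of these would serve:

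- PROC MIXED with REPEATED / GROUP=trt01pn and Satterthwaite or Kenward-Roger degrees of freedom
- HC3 standard errors

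Report the PROC GLM result as a sensitivity analysis. Apply the same rule to the pooled-group ANCOVA. Protocol 8.5.1 needs no change. A sentence in SAP 3.7 confirming that the substituted values feed DAVG7 would remove the ambiguity noted above.

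The cost is a few lines of SAS and a sentence or two of SAP text. If the variances are in fact equal, the standard error is about 2% larger (0.228 against 0.223; 0.228/0.223 = 1.02). Settling this in advance also avoids choosing between standard errors once results by arm are known.

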8.5.2. Secondary Analyses

The proportion of participants all-cause MAV (medical visits attended in person by the participant and a health care professional) or death by Day 28 will be estimated using Kaplan-Meier methods by treatment group in Part C. The proportion of participants COVID-19 related MAVs or death by Day 28 will be estimated using Kaplan-Meier methods by treatment group in Part C. The proportion of hospitalization by Day 28 will be summarized by treatment group. Kaplan Meier product limit method will be used to estimate time to negative SARS-CoV-2 PCR and time to alleviation (mild or absent) of baseline COVID-19 symptoms by treatment group.

8.6. Safety Analysis

All safety data collected on or after the randomization date through Day 28 will be summarized by treatment group (according to the study treatment received). Data for the pretreatment will be included in data listings.

8.6.1. Extent of Exposure

A subject's extent of exposure to study treatment data will be generated from the study treatment administration data. Exposure data will be summarized by treatment group.

8.6.2. Adverse Events

Clinical and laboratory AEs will be coded using the Medical Dictionary for Regulatory Activities (MedDRA). System organ class, high-level group term, high-level term, preferred term (PT), and lower-level term will be attached to the clinical database.

Events will be summarized on the basis of the date of onset for the event. A TEAE will be defined as any AE that begins on or after the date of first dose of study treatment up to the date of last dose of study treatment plus 30 days.

Summaries (number and percentage of subjects) of TEAEs (by system organ class and PT) will be provided by treatment group.

8.6.3. Laboratory Evaluations

Selected laboratory data will be summarized using only observed data. Data and change from baseline at all scheduled time points will be summarized.

Graded laboratory abnormalities will be defined using the grading scheme in DAIDS Table for Grading the Severity of Adult and Pediatric Adverse Events, Version 2.1 dated July 2017.

Incidence of treatment-emergent laboratory abnormalities, defined as values that increase at least 1 toxicity grade from baseline at any time post baseline up to the end date of the study, will be summarized by treatment group. If baseline data are missing, then any graded abnormality (ie, at least a Grade 1) will be considered treatment-emergent.

Laboratory abnormalities that occur before the first dose of study treatment or after the subject has been discontinued from treatment for more than 30 days will be included in a data listing.

8.7. Adjustments for Multiplicity

No adjustments for multiple comparison are planned.

8.8. Pharmacokinetic Analysis

For Parts A and B, plasma concentrations and PK parameters (if applicable) for inhaled RDV and its metabolites will be listed and summarized using descriptive statistics by treatment group (including mean, geometric mean, median, minimum, maximum, and sample size). Concentrations of inhaled RDV and its metabolites in plasma over time will be summarized. For Part C, plasma concentration of GS-441524 will be listed and summarized using descriptive statistics by nominal time.

8.9. Sample Size

The sample size in this study is determined based on practical considerations and past experience with similar types of studies. No sample size/power calculation was performed. A sample size up to approximately 152 participants (72 participants for Part A and Part B; 80 participants for Part C) should provide a suitable assessment of the descriptive efficacy, and safety profile in this population.

